11.6.2.4. Cosmetic acceptability

Subjects will complete a cosmetic acceptability questionnaire concerning the cosmetic product at the last visit.

The following items will be evaluated by the subjects:

| | ITEMS |
|----|---|
| 1 | Le produit est facile à étaler The product is easy to spread |
| 2 | Le produit est facile à appliquer The product is easy to apply |
| 3 | Le produit pénètre vite The product penetrates quickly |
| 4 | La couleur du produit est agréable The color of the product is pleasant |
| 5 | L'odeur du produit est agréable The scent of the product is pleasant |
| 6 | L'aspect du produit est agréable The aspect of the product is pleasant |
| 7 | La texture du produit est agréable The texture of the product is pleasant |
| 8 | La texture est confortable The texture is comfortable |
| 9 | Le produit ne laisse pas la peau collante The product doesn't leave the skin sticky |
| 10 | Le produit ne laisse pas de film gras sur la peau The product doesn't leave a greasy film on the skin |
| 11 | Le produit laisse un effet soyeux The product leaves a silky effect |
| 12 | Le produit ne peluche pas The product does not go noodles |

The following scale will be used:

- Agree (“D'accord”)
- Somewhat agree (“Plutôt d'accord”)
- Neither agree, nor disagree (“Ni d'accord ni pas d'accord”)
- Somewhat disagree (“Plutôt pas d'accord”)
- Disagree (“Pas d'accord”)

11.6.2.5. Microbiota analysis (6)

a) Sampling:

At W0 (before any application) and at W12 (after a 12-week application period), microbiota sampling will be performed by the same sampler (technician or nurse).

Skin microbiota sample will be collected on one test site of 4 cm² (square of 2 cm x 2 cm) which will be delineated using a template (to ensure that the same area will be sampled at each visit) on the middle of the left cheek and using aseptic techniques under sterile airflow generated by a portable hood.

Single use sterile square-sized cotton-tipped swabs (165KS01, COPAN SPA, Brescia, Italy) will be moistened with a sterile solution (filtered at 0,22 microns before use) of deionized water containing 0.15 M NaCl and 0.1% Tween 20.

Cotton tips containing the samples will be stored at -80°C until the end of the study and shipped for processing using dry ice to INRA Transfert.

b) Analysis (if applicable):

According to the results of the primary variable, the Sponsor will decide to go ahead with the microbiota analysis which will be done by INRA Transfert.

DNA Extraction, PCR Amplification, and Sequencing

DNA will be extracted from the swabs using the MoBio PowerSoil-htp 96-well Soil DNA Isolation Kit (MoBio, Inc., Carlsbad, CA, USA) following the manufacturer's instructions. PCR amplification will be performed for each DNA sample. DNA will be PCR amplified with barcoded primers that targets the V1-V3 region of bacterial. Cleaned pools will be sequenced on the Illumina MiSeq platform at Genotoul Next Generation Sequencing Facility, France.

Sequence Processing

Sequences will be processed as previously described. Sequences will be then de-replicated and a database containing one sequence for each operational taxonomic unit (OTU) will be generated at the 97% nucleotide identity level. Sequencing reads from the full dataset will be then clustered to the database to generate an OTU table. Taxonomy will be assigned to each OTU using Greengene database.

Interpretation of these results will be done by Mercurialis.

11.6.2.6. Safety: Adverse Events Collection

All AE reported during the study will be recorded in the CRF.

11.7. Adverse events and serious adverse events

11.7.1. Adverse events

11.7.1.1. *Definition of adverse events*

An **adverse event** is any untoward medical occurrence in a subject who has been administered an IP, which does not necessarily have a causal relationship with this IP.

An **Adverse Event** (AE) can therefore be any unfavourable and unintended sign (including an abnormal laboratory finding), symptom, or disease temporally associated with the use of an IP, whether or not related to the IP.

Thus any new sign, symptom or disease, or clinically significant increase in the intensity of an existing sign, symptom or disease, should be considered as an adverse event.

Notes:

- Clinically significant worsening of the disease/condition being evaluated, which occurs during the study, may be considered as an adverse event according to the Dermatologist judgment.
- Lack of efficacy of the IP is not considered an adverse event unless it leads to other unfavourable medical occurrence.
- Any new sign or symptoms suffered by the subject as results of accidental or intentional overdose or misuse of the IP should be reported as an adverse event. The overdose itself is not an adverse event.
- Pregnancy is not per se an adverse event. Any incidents of pregnancy during a study will be reported to the Sponsor immediately by letter to the Sponsor. The Sponsor will advise on the appropriate course of action. The subject will be immediately withdrawn from the study and the pregnancy will be documented as required by the protocol.
- Planned hospitalisation for elective treatment of a pre-existing condition that has not worsened from baseline is not considered an AE.

The expected AE of the drug treatment are listed in the “Résumé des Caractéristiques du Produit” (cf Appendix 4).

11.7.1.2. *Reporting of adverse events*

Events reported by the subject, or observed by the investigator, should be described in the following manner.

The **NATURE** of the event should be described in precise, standard medical terminology (i.e., not necessarily the exact words used by the subject). Where possible, a specific diagnosis should be stated (e.g., allergic contact dermatitis).

TIME OF THE EVENT will be described by the terms:

- Onset date (ie the date the first symptoms were experienced by the subject or the date the AE was discovered)
- End date (or left blank for event not resolved at the end of the follow up).

SERIOUSNESS of the event will be described by the terms:

- Minor i.e. not serious
- Serious

CAUSAL RELATIONSHIP of the event to the use of the IP will be according to the investigator's clinical judgement and described by the terms:

- Not related The event is clearly related to other factors such as the subject's clinical state, therapeutic interventions, or concomitant medications administered to the subject or no IP has been used (where applicable)
- Unlikely The event was most likely produced by other factors such as the subject's clinical state, therapeutic interventions, or concomitant medications administered to the subject; and do not follow a known response pattern to the IP.
- Possible The event follows a reasonable temporal sequence from the time of IP administration; and/or follows a known response pattern to the study treatment; but could have been produced by other factors such as the subject's clinical state, therapeutic interventions, or concomitant medications administered to the subject.
- Probable The event follows a reasonable temporal sequence from the time of IP administration; and follows a known response pattern to the IP; and cannot be reasonably explained by other factors such as the subject's clinical state, therapeutic interventions, or concomitant medications administered to the subject.
- Definite As for Probable AND either occurs immediately following IP administration, or improves on stopping the IP, or reappears on repeat exposure, or there is a positive reaction at the specific application site.
- Unknown There is insufficient information to make a judgment

ACTION WITH RESPECT TO IP will be described by the terms:

- None
- Discontinue product (the subject continues on the study, if the protocol allows it, with or without re-introduction of the IP)
- Adjust dosage if the protocol allows it
- Withdraw from study

CORRECTIVE TREATMENT to be reported as a concomitant medication.

- None
- Medication
- Non-medication therapy

FREQUENCY of the event

- Isolated
- Intermittent
- Constant

SEVERITY of the event will be described in terms of mild, moderate or severe according to the investigator's clinical judgement.

- Mild: Did not interfere with normal everyday activities
- Moderate: Interfered to some extent with everyday activities
- Severe: Was not tolerated and interfered with normal everyday activities

EXPECTED / UNEXPECTED will be described by the terms:

- Expected AE conforms with known AEs associated with the IP as described in the supporting literature (i.e. Investigator Brochure)
- Unexpected

IMMEDIATE OUTCOME and FOLLOW UP OUTCOME of the event will be described by the terms:

- Ongoing
- Resolved
- Stabilized / discharged
- Lost to follow up (except for immediate outcome)

During the subject's study participation, all adverse events should be followed up to determine the final outcome. When an AE persists at the end of the subject's participation in the study, follow-up will be required for those adverse events classified as "possible", "probable" or "definite" related to the IP.

Follow-up should continue until

- the event has resolved or,
- the event is considered to be stabilized (at discretion of investigator and/or Sponsor) or,
- the subject has been discharged to the care of their own physician

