11.7.2.2. Reporting of serious adverse events

Any Serious Adverse Event (SAE), related or unrelated to any IP or procedures occurring after informed consent has been obtained, and until the subject's completion of the study, must be reported to the Sponsor within ONE working day of the investigator becoming aware of the event. This may be done by email or telephone call.

SAEs must be reported using a Serious Adverse Event (SAE) form. The information provided on the form must include a description of the clinical course of the SAE and an assessment of the intensity, causal relationship to the IP and/or study procedures, the action taken and the outcome to date.

Reporting and completed SAE form must be emailed to the Sponsor:

[name]
Medical Director
[name]
[contact]
E-mail: [contact]

The initial report should be followed by a detailed description as more information becomes available which may include copies of hospital records and other documents when requested and applicable.

If an investigator is in doubt whether to regard an adverse event as serious or not, the event is to be considered as serious until otherwise established.

All SAEs and Suspected, Unexpected Serious Adverse Reactions (SUSARs) are subject to expedited reporting to competent authorities and CPP and all concerned investigators, unless otherwise required as per local requirements.

For all SAEs, the investigator will follow-up the final outcome and ensures all queries have been resolved. Details of follow-up should be recorded (e.g. discontinuation of IP, if specific treatment is required, if hospitalisation is required etc.).

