Physical and functional signs will be described and analysed using a generalized linear random model for multinomial data (a model for binary data can also be used according to the results of the descriptive analysis), with Subject as random factor, Time and Product as fixed factors (SAS® Glimmix Procedure).

The overall tolerance will be compared between treatments using a chi-square test.

The adverse events will be described and the number of subjects with at least one AE related to the study product will be compared between products by a chi-square test.

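### Non-serious adverse events of Unknown causality that persist at the end of participation fall outside the required follow-up

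*Combined protocol and SAP*

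**What the plan says.** Section 11.7.1.2 asks the investigator to rate causality as Not related, Unlikely, Possible, Probable, Definite or Unknown. The last is defined as "Unknown There is insufficient information to make a judgment".

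The same section has two follow-up rules. While the subject is in the study: "During the subject's study participation, all adverse events should be followed up to determine the final outcome". For an event that persists when participation ends, "follow-up will be required for those adverse events classified as" possible, probable or definite in relation to the product. Follow-up then runs until the event resolves, is considered stabilised, or the subject is discharged to their own physician.

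Serious events have a separate rule in section 11.7.2.2: "For all SAEs, the investigator will follow-up the final outcome and ensures all queries have been resolved". It has no causality condition.

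Section 9.6 states that no follow-up is planned for withdrawn subjects, and lists an adverse event among the reasons for withdrawal.

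Section 11.6.2.6 has every reported adverse event entered in the CRF. Section 14.3 says "The adverse events will be described", and then that "the number of subjects with at least one AE related to the study product will be compared between products by a chi-square test". It does not say which of the six terms make an event related.

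**The concern.** Not related and Unlikely record a judgment that something else caused the event. Unknown records that no judgment could be made. Giving all three the same treatment after the end of participation means that the one category defined by missing information is not among those for which more information must be sought.

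The timing makes this more than a wording point. Under section 10.4 the products are applied until the day before the W12 visit. For an event still ongoing at W12 in a subject who has used the products throughout, what happens after stopping can be seen only after participation ends. Improvement on stopping is one of the features that section 11.7.1.2 uses to separate Definite from Probable.

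At stake is the completeness of the safety information, whose collection is a secondary objective (section 7.2). To a lesser degree, the clarity of the one adverse event comparison that is tested is also at stake.

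**Working it through.** The point turns on the text, and there is no figure in the plan to reproduce. Set side by side, sections 11.7.1.2 and 11.7.2.2 give:

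| Causality term | During participation | Persisting at the end, non-serious | Serious |
|---|---|---|---|
| Not related | followed | not required | followed to final outcome |
| Unlikely | followed | not required | followed to final outcome |
| Possible | followed | required | followed to final outcome |
| Probable | followed | required | followed to final outcome |
| Definite | followed | required | followed to final outcome |
| Unknown | followed | **not required** | followed to final outcome |

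Only one cell is in question: non-serious, Unknown, and still ongoing when participation ends.

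**Withdrawn subjects.** Section 9.6 plans no follow-up for them. Section 11.7.1.2 requires it for a persisting event rated possible, probable or definite, and section 11.7.2.2 requires it for every serious event. Neither makes an exception for withdrawal. These sections conflict whatever is done about Unknown, and adding Unknown to the list would not by itself settle what happens to a withdrawn subject.

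**The related comparison.** Section 14.3 tests subjects with at least one related event but does not map *related* to the six terms. To see whether the missing definition could matter, take assumed counts, since the documents give no event rates. Use 100 per arm (section 9.1) and a Pearson chi-square without continuity correction, which for equal arms is z² with

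z = (p₂ − p₁) / √[p̄(1 − p̄) × 2/100], where p̄ = (p₁ + p₂)/2.

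Starting point 10/100 versus 20/100: p̄ = 0.15, z = 0.10/√(0.15 × 0.85 × 0.02) = 0.10/0.0505 = 1.98, p = 0.048.

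| Unknown subjects counted as related | Counts | p |
|---|---|---|
| none | 10 v 20 | 0.048 |
| 1 in the lower arm | 11 v 20 | 0.079 |
| 3 in the lower arm | 13 v 20 | 0.18 |
| 5 in the lower arm | 15 v 20 | 0.35 |
| 1 in the higher arm | 10 v 21 | 0.032 |
| 3 in the higher arm | 10 v 23 | 0.013 |
| 2 in each arm | 12 v 22 | 0.060 |

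Each reclassified subject moves an arm's rate by 1/100, or 1 percentage point. In a case chosen to be borderline, the convention can move the result across 5%, and it can move p either way. The table shows that a definition is worth having. It says nothing about what will happen in this trial.

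**The case against.** The strongest reply is that little falls through the gap. Every event is recorded, described, and followed during participation, and every serious event is followed to its outcome. Section 11.7.2.2 also treats doubtful cases as serious. Possible is broad: a reasonable time sequence or a known response pattern is enough, even if other causes could explain the event. Many ongoing skin reactions would therefore be rated Possible and followed, leaving Unknown as a residual category. The reactions most relevant to a facial product (erythema, dryness, scaling, tightness, prickling, itching, burning) are scored at every visit and analysed with no causality filter (sections 11.6.2.3 and 14.3). The follow-up list is also a minimum and does not stop an investigator from following other events. All of this stands, and it limits the importance of the point. It does not explain why the category defined by insufficient information is left off the list.

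A reader might go further in three ways that the documents do not support.

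- *Unknown events are dropped.* They are not: they are recorded, described and followed during participation.
- *Unknown counts as not related in the comparison.* Section 14.3 neither includes nor excludes it. Carrying over the three terms from section 11.7.1.2 is an inference from a follow-up rule, which is not an analysis definition. A SAP is still to be written and approved before database lock (sections 13.3 and 14), and such a mapping can be set there.
- *The related-event rate is biased downward.* That needs both the inference above and the assumption that Unknown events are truly due to the product. The trial is double-blind, both arms use the same drug treatment, and nothing in the documents suggests that Unknown would be used more in one arm.

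**Conclusion.** The point holds in a limited form. A non-serious adverse event rated Unknown that persists at the end of participation is outside the required follow-up in section 11.7.1.2, although follow-up is how its causality could be clarified. This rests on the wording alone and needs no numerical assumption. The number of events affected cannot be estimated, because the documents give neither adverse event rates nor the expected use of Unknown. No direction or size of bias in the related-event comparison can be claimed.

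The missing definition of *related* in section 14.3 is a detail for the pending SAP and is secondary. The conflict over withdrawn subjects is a separate inconsistency that bears on the same events. Overall this is a minor, inexpensive improvement and no threat to the trial's conclusions.

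**What to change.** 1. In section 11.7.1.2, add Unknown to the causality categories that require follow-up after the end of participation, and have causality reassessed and recorded at that follow-up. The cost is a few extra contacts, bounded by the stopping points already in that section.
2. Reconcile section 9.6 with sections 11.7.1.2 and 11.7.2.2, so that it is clear what follow-up of adverse events applies to withdrawn subjects. This is a text change.
3. In the SAP, before the code is broken (section 9.5.2 places this after database lock, apart from emergency opening for a serious event), state which causality terms count as related in the section 14.3 comparison. Add a sensitivity analysis that counts events still Unknown the other way. Which way the main definition goes is debatable: counting Unknown as related could add events not due to the product to both arms. What matters is that the choice is written down in advance and both results are shown. The cost is one definition and one additional result.

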11.7.2. Serious adverse events

11.7.2.1. Definition of serious adverse events

Serious Adverse Event (SAE): Any untoward medical occurrence that at any dose:

- results in death,
- is life-threatening,
- requires insubject hospitalisation or prolongation of existing hospitalisation,
- results in persistent or significant disability/incapacity or
- is a congenital anomaly/birth defect

or

- other medically important conditions*

* Medical and scientific judgement should be exercised in deciding whether expedited reporting is appropriate in other situations, such as important medical events that may not be immediately life threatening or result in death or hospitalisation but may jeopardise the subject or may require intervention to prevent one of the other outcomes listed in the definition above. These should also usually be considered serious.

11.7.2.2. Reporting of serious adverse events

Any Serious Adverse Event (SAE), related or unrelated to any IP or procedures occurring after informed consent has been obtained, and until the subject's completion of the study, must be reported to the Sponsor within ONE working day of the investigator becoming aware of the event. This may be done by email or telephone call.

SAEs must be reported using a Serious Adverse Event (SAE) form. The information provided on the form must include a description of the clinical course of the SAE and an assessment of the intensity, causal relationship to the IP and/or study procedures, the action taken and the outcome to date.

Reporting and completed SAE form must be emailed to the Sponsor:

[name]
Medical Director
[name]
[contact]
E-mail: [contact]

The initial report should be followed by a detailed description as more information becomes available which may include copies of hospital records and other documents when requested and applicable.

If an investigator is in doubt whether to regard an adverse event as serious or not, the event is to be considered as serious until otherwise established.

All SAEs and Suspected, Unexpected Serious Adverse Reactions (SUSARs) are subject to expedited reporting to competent authorities and CPP and all concerned investigators, unless otherwise required as per local requirements.

For all SAEs, the investigator will follow-up the final outcome and ensures all queries have been resolved. Details of follow-up should be recorded (e.g. discontinuation of IP, if specific treatment is required, if hospitalisation is required etc.).

11.7.2.3. Pregnancy

Pregnancy which occurs during a study with an IP must be reported to the Sponsor by use of the Serious Adverse Event (SAE) Form and handled as a SAE with regard to reporting time frame. All pregnancies must be followed-up until conclusion.

11.7.3. Vigilance

- The suspicions of serious adverse event,
- The suspicions of other adverse events where a medical treatment was required and those that seem to have a serious nature,
- The new facts,

Will have to be declared to ANSM by the Sponsor according to article of law R.1123-49 of the "Code de la Santé Publique".

12. CODE AND HANDLING OF SAMPLES

12.1. Samples coding

Samples for microbiota analysis will be coded as follows:

- Study number (VCA 18-01)
- the randomisation number (RD1001 to RD1100 & RD2001 to RD2100),
- the visit (W0, W12)

12.2. Sample collection -preparation-storage and transfer

Cotton tips containing the samples will be stored in dry ice, then at -80°C (± 5) in each study centre until their shipment to INRA Transfert, for analysis (if applicable).

12.3. Remaining samples and archive samples

Remaining of samples will be destroyed by:

- INRA Transfert if analysis will be done
- Each centre if no analysis will be done.

13. DATA MANAGEMENT

13.1. Database set up

The data collection system (including database and data entry screens) is specifically designed with Ennov Clinical software for recording the data required by the protocol. The data entry system will be developed by SYLIA-STAT LANCRENON.

